Table XIV.5b Responder Analysis at Study Time Points in Sub-group with EF \geq 25 and NYHA = 3

Variable	Time	Control n/N (%)	Optimizer n/N (%)	P-value ¹
MLWHFQ ²	24 Week	35/84 (41.67)	60/101 (59.41)	0.0119
	50 Week	28/76 (36.84)	61/97 (62.89)	0.0006
NYHA ³	24 Week	19/82 (23.17)	43/97 (44.33)	0.0023
	50 Week	32/77 (41.56)	51/99 (51.52)	0.1229
6 MWT ⁴	24 Week	20/79 (25.32)	36/97 (37.11)	0.0652
	50 Week	22/70 (31.43)	35/95 (36.84)	0.2895

¹One-sided Fisher's Exact Test

²Responder is a 10 or more point improvement from baseline.

³Responder is a 1 or more point improvement from baseline.

⁴Responder is a 40 or more meters improvement from baseline.

These analyses indicate that for CC patients with EF \geq 25 and NYHA = 3, Optimizer patients have greater response than control patients and it is significantly greater for MLWHFQ and NYHA at 24 weeks and for MLWHFQ at 50 weeks with a P<0.025.

These additional analyses indicate that Optimizer patients had greater changes from baseline than control patients across all measures. Statistical significance in responder analyses with P-values less than 0.025 was achieved for all Optimizer CC patients for MLWHFQ overall at 24 and 50 weeks and NYHA for 24 weeks. For patient sub-grouped with EF \geq 25 whether or not the NYHA =3, the AT responder analysis demonstrated superiority for the Optimizer patients with P-values less than 0.025 at both 24 and 50 weeks. In these patients, the PVO2 demonstrated a significant advantage for Optimizer patients at 24 weeks.

References:

1. Meinert, C. (1986). *Clinical Trials: Design, Conduct, and Analysis*. Oxford University Press, New York.
2. Hosmer, D. and Lemeshow, S. (2000). *Applied Logistic Regression (Second Edition)*. John Wiley and Sons, New York.
3. Rubin, D. (1987). *Multiple Imputation for Nonresponse in Surveys*. John Wiley and Sons, New York.

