Individual patient response will be defined as an increase of ≥ 1 **ml O₂/kg/min** in VT at 6 months as compared with baseline. Responder rates will be calculated and compared between the treatment and control groups based on both the intent-to-treat population and the per-protocol population using a one-sided binomial comparison with an alpha of 0.025.

The statistical hypothesis to be tested is:

$$H_0: \pi_c \geq \pi_t \quad \text{vs.} \quad H_A: \pi_c < \pi_t$$

Where π_c is the proportion of patients in the control group that have ≥ 1 ml O₂/kg/min improvement in VT at 6 months from baseline and π_t is the proportion of patients in the treatment group that have ≥ 1 ml O₂/kg/min improvement in VT at 6 months from baseline.

2. Primary Safety Analysis

The primary safety analysis shall evaluate the composite event rate of all cause mortality and all cause hospitalization at 12 months. The statistical hypothesis shall be that the proportion of patients in the treatment group where an event occurs by 12 months will be non-inferior to the proportion of patients where an event occurs by the 12 month visit in the control group.

The statistical hypothesis to be tested shall be:

$$H_0: \pi_t > \pi_c + \delta$$

vs.

$$H_1: \pi_t \leq \pi_c + \delta$$

where $\delta=0.125$ (clinically insignificant difference) and π_c is the event rate in the control group and the π_t is the event rate in the treatment group.

The statistical test to be used shall be the Blackwelder non-inferiority test and will be evaluated based on the intent-to-treat patient population and the per protocol patient population. Censoring is expected to be minimal, but in order to determine if there are different patterns of mortality between groups, Kaplan-Meier curves will also be constructed, with Log-rank tests used to determine statistical significance between groups.

The nature, frequency, and seriousness of adverse events between the two groups shall be compared using descriptive summary statistics.

3. **Justification of sample size**

Results of prior studies of CCM and biventricular pacing in which VT has been employed as an endpoint provide estimates for standard deviations of changes and standard deviations of absolute values that may be observed in the present study.

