²Pseudo-sites were used in this analysis and are defined in Table 4a.

Table VI.8 Summary of Study Site Comparability¹ for Baseline Medications.

Variable	P-value for Treatment	P-value for Study Site ²	P-value for Site by TRT Interaction
ACEi	0.1089	0.5171	0.0226
ARB	0.4673	0.3345	0.4238
ACEi +/- ARB	0.0518	0.0191	0.0261
B-Blocker	0.5372	0.1887	0.6063
Diuretic	0.4026	0.9576	0.4637
Second Diuretic	0.0122	0.0035	0.0161
Aldosterone Inhibitor	0.1551	0.7007	0.2385
Antiarrhythmic	0.2260	0.3131	0.5036
Hydralazine	0.5334	0.9813	0.7634
Nitrates	0.8873	0.3973	0.6726
Ca Channel Blocker	0.2411	0.3480	0.9998

¹Analysis by logistic regression.

²Pseudo-sites were used in this analysis and are defined in Table 4a.

Table VI.9 Summary of Study Site Comparability¹ for Baseline Cardiopulmonary Exercise

Variable	P-value for Treatment	P-value for Study Site ²	P-value for Site by TRT Interaction
Duration (minutes)	0.4822	0.0022	0.2157
Peak SBP (mmHg)	0.7493	<0.0001	0.5936
Peak HR (bpm)	0.4134	0.0223	0.4897
Peak VO2 (ml/kg/min)	0.9894	0.6534	0.5938
Peak RER	0.7288	0.0020	0.9477
AT (ml/kg/min)	0.9690	0.3116	0.4726

¹Analysis by general linear models analysis of variance with Type III sums of squares.

²Pseudo-sites were used in this analysis and are defined in Table 4a.

Because several baseline variables were significantly different between study sites, study pseudo-site will be used as a possible covariate in multivariate analyses below.

VII. Study Populations

The analysis populations are the intention to treat (ITT) consisting of all subjects randomized. The full analysis set A (FASA), consisting of all randomized patients but excluding patients who never received a study treatment (there were 7 Optimizer and 1 Control patient excluded in this population). The full analysis set B (FASB) consisting of all randomized patients excluding patients who did not receive a study treatment or had no study follow-up (there were 7 Optimizer and 6 Control patients excluded from this population). The population of completed cases (CC) consisting of all patients with a 24 week endpoint. The final population is the per protocol (PP) consisting of all CC patients who did not have a protocol violation that would

substantially affect study outcomes. Imputation by the methods described below is used to provide outcomes for effectiveness for subjects without outcomes in the ITT and FAS populations.

VIII. Comparison of Patient with Missing and Non-Missing Data

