A comparison of the baseline characteristics between patients with missing data for the primary effectiveness variable and those without missing data are provided below. These test are intended to determine if there is evidence of not missing at random and if there is, to provide a remedy such that the missing data can be assumed to be missing at random for those patients for which imputation is planned. An initial analysis indicated that baseline weight, BMI, and site and core laboratory exercise durations were statistically significant. The weight variable was considered of lower importance, but the exercise duration could impact anaerobic threshold (AT, the primary effectiveness variable) and therefore indicated that, strictly speaking, the data are not missing at random. A review of the data indicated that the vast majority of exercise times exceeded 6-7 minutes and that subjects with short exercise times were less likely to show an improved AT regardless of treatment group. On that basis, any patient missing the 24 week PVO2 and/or 24 week AT was assigned a worst case score. This is similar to patients who had an event, i.e, patients who died or had an intervention (LVAD, heart transplant, or surgery to correct CHF) at a time that could be considered the reason why the data for 24 weeks was missing. There were 10 Active and 4 Control patients who had events prior to the 24 week visit and there were 3 Active and 6 Control patients who had an event between 24 and 50 weeks such that the event was considered the reason for missing the 24 week CPX. The inclusion of patients with missing 24 week data and a baseline core laboratory exercise time of less than 6.5 minutes results in 5 Active and 8 Control patients added to the worst score assignment list. The cumulative result is that 18 Active and 18 control patients had either the lowest AT value from any previous visit assigned, or if all AT values were missing for previous visits, the lowest AT value recorded for any randomized patient. These patients are indicated in Table IX.1 below as Imputation Case 6.

After removing the 13 cases with missing 24 week data and an exercise time less than 6.5 minutes, the baseline characteristic comparison between patients with missing and non-missing data at 24 weeks or baseline are presented in the following tables.

Table VIII.1 Baseline Demographics – Quantitative Variables - Compare Patients with Missing 24 Week AT data with those Not Missing 24 Week Data

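### The efficacy per-protocol set requires a 24-week value, so patients whose death, LVAD, transplant or heart failure surgery explains the missing test are excluded by outcome; the numerical effect is small, but the definition should change

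*Combined protocol and SAP*

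**What the plan says.** Protocol Section IX.A.1 compares responder rates "based on both the intent-to-treat population and the per-protocol population using a one-sided binomial comparison with an alpha of 0.025". It does not define the per-protocol population.

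The statistical report does so in Section VII. It first defines completed cases: "The population of completed cases (CC) consisting of all patients with a 24 week endpoint". It then builds PP from them: "The final population is the per protocol (PP) consisting of all CC patients who did not have a protocol violation", the violation being one that would materially affect outcomes. Imputation is provided only to supply "outcomes for effectiveness for subjects without outcomes in the ITT and FAS populations", so neither CC nor PP receives imputed values.

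Section VIII describes the event patients: "patients who died or had an intervention (LVAD, heart transplant, or surgery to correct CHF) at a time that could be considered the reason" for the missing 24-week data. It counts them in two steps. First: "There were 10 Active and 4 Control patients who had events prior to the 24 week visit". Then, where the later event was judged to explain the missing exercise test: "there were 3 Active and 6 Control patients who had an event between 24 and 50 weeks". In the ITT analysis these patients are part of Imputation Case 6 (18 per arm) and "had either the lowest AT value from any previous visit assigned, or if all AT values were missing for previous visits", the lowest AT of any randomised patient.

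Section X uses PP differently for safety. It starts from the modified ITT set and removes one Control violator and four Optimizer patients who refused treatment, leaving 206 and 204. No 24-week value is needed.

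**The concern.** A per-protocol set is meant to remove departures from the protocol. Death, LVAD implantation, transplant or corrective surgery is not a departure; for an exercise-response endpoint it is a failure. Under Section VII such a patient leaves PP because the outcome prevented the measurement. The two populations named for the primary test then differ in more than adherence: ITT counts these patients as failures, while PP describes only patients who lived and could be tested.

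More of these patients are in the device arm, so their removal tends to favour the device. The same applies to the completed-case AT responder tables in Sections XIII and XIV. One of those supports a claim with little room to spare: EF≥25 at 24 weeks, P=0.0230 against 0.025.

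**Working it through.** **Inputs.** Completed-case AT responders at 24 weeks (Table XIII.1b, at least 20% rise): Optimizer 28/159, Control 18/154. Event patients (Section VIII): before week 24, 10 Active and 4 Control; later, 3 and 6; total 10+3=13 and 4+6=10. All Case 6 patients: 18 and 18. EF≥25 completed cases (Table XIV.2b): 17/88 and 6/79.

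**Step 1. Reproduce the printed figure.** 28/159 = 17.61%; 18/154 = 11.69%; difference 5.92 points; risk ratio 1.507; one-sided Fisher P = 0.0932. This matches the report.

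**Step 2. Count event patients as non-responders.** Numerators stay fixed and the event patients join the denominators. This follows the ITT rule: a patient carrying the lowest earlier AT does not show a 20% rise.

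| Added (Active/Control) | Optimizer | Control | Difference (points) | Risk ratio | One-sided P |
|---|---|---|---|---|---|
| none | 28/159 (17.61%) | 18/154 (11.69%) | 5.92 | 1.507 | 0.0932 |
| 13/10, all event patients | 28/172 (16.28%) | 18/164 (10.98%) | 5.30 | 1.483 | 0.1045 |
| 10/4, before week 24 only | 28/169 (16.57%) | 18/158 (11.39%) | 5.18 | 1.454 | 0.1176 |
| 18/18, all Case 6 | 28/177 (15.82%) | 18/172 (10.47%) | 5.35 | 1.512 | 0.0931 |

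For 13/10 the fall is 5.92 − 5.30 = 0.62 points, about 10% of the completed-case difference.

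**Step 3. Separate dilution from imbalance.** The event share is 13/172 = 7.6% in Active and 10/164 = 6.1% in Control; pooled, 23/336 = 6.8%. Equal dilution of both arms by 6.8% would alone take 5.92 to 5.92 × (1 − 0.068) = 5.52 points. That is 0.40 of the 0.62-point fall, about two-thirds. Only the rest comes from the uneven loss.

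**Step 4. EF≥25 at 24 weeks.** 17/88 against 6/79 reproduces P = 0.0230. Event counts by EF are not reported, so each split below is an assumption.

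| Assumed events in EF≥25 (Active/Control) | Optimizer | Control | One-sided P |
|---|---|---|---|
| 5/2 | 17/93 | 6/81 | 0.028 |
| 7/5 | 17/95 | 6/84 | 0.0258 |
| 5/4 | 17/93 | 6/83 | 0.0243 |
| 7/6 | 17/95 | 6/85 | 0.0241 |

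The 5/2 and 7/5 splits are 10/4 and 13/10 scaled by the subgroup's share of each arm (117/215 = 54% and 113/213 = 53%). The result falls on either side of 0.025.

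**The case against.** The strongest reply is that nothing in the report rests on PP for efficacy. Section XII presents ITT, FASA and FASB only, and PP counts appear only for safety. The figures above therefore come from a stand-in, and under the report's 20% criterion rather than the protocol's 1 ml O₂/kg/min. This stands: the size of any PP bias cannot be read from the documents. The rule itself is nevertheless written down, for a population that the protocol names for the primary test.

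A second reply is that the loss is not lopsided. A reader might infer a strong differential bias from the 10 against 4 events before week 24. The same sentence of Section VIII adds 3 Active and 6 Control, giving 13 and 10, and the full worst-score list is 18 and 18, at which P is unchanged. Absence from completed cases for any reason is 215 − 159 = 56 Active and 213 − 154 = 59 Control. This also stands, and it is why the effect is called small.

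A third reply is that FASB (207 Control, 208 Optimizer), with event patients worst-scored and the rest imputed, is already close to an adherence-based set. Its printed whole-population P is 0.3100. The EF≥25 ITT result (P = 0.0260) is openly described as slightly above 0.025. This is fair, and it makes the correction cheap. It does not settle what PP means, nor does it qualify the completed-case EF≥25 statement in Section XIV, which is repeated in the closing paragraph.

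Finally, membership is not fully traceable: Table IX.1 lists 153 Controls with complete data, while the completed-case table has 154.

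**Conclusion.** The point holds as a fault of definition with a small numerical effect. The efficacy PP set selects on outcome, contrary to the report's own ITT scoring and to the way it forms PP for safety. On the completed-case stand-in, correcting this lowers the difference by about 0.6 points, from 5.92 to 5.30 (range 5.18 to 5.35). The result is non-significant at 0.025 before and after, and the whole-population conclusion is unchanged.

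Two stronger readings are not supported. A reader might infer that the device effect in PP is overstated by some 12%. That is 5.92/5.30 − 1 = 11.7%, a relative figure for a gap of 0.62 points, mostly dilution, taken from a table that is not PP; on the risk ratio the change is under 2%. A reader might also infer that the EF≥25 finding is lost. The assumed splits show only that P = 0.0230 is fragile.

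The estimate assumes that event patients are non-responders, that none is already among the completed cases, and that completed cases resemble PP. Some of the 13 Active patients may be among the seven Optimizer patients who never received treatment; an adherence-based PP would properly omit those.

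**What to change.** 1. Define the efficacy PP by adherence only: assigned treatment received and no major violation, without requiring a 24-week value. Reconcile it with the safety PP so that the term has one meaning. The modified ITT set behind the safety PP also drops patients who died or withdrew early without follow-up; state explicitly how early deaths are handled.
2. Count patients whose death, LVAD, transplant or heart failure surgery explains the missing 24-week test as non-responders in the PP and completed-case AT responder analyses. Impute other missing values in PP by the ITT method.
3. Report event counts by arm and EF subgroup, and print the PP efficacy result.
4. Restate the 24-week EF≥25 completed-case claim in Section XIV and its closing paragraph on that basis.

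The cost is one change of definition and a re-run of existing tables. No new data are needed. The whole-population estimate is likely to be slightly less favourable to the device, and the EF≥25 claim may or may not stay below 0.025.

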Any FIX-HF-5 Study Investigator not participating in the FIX-HF-5C Study that wishes to use an OPTIMIZER IVs IPG for a revision/replacement procedure must request an “Approved Deviation From Protocol” from their IRB, the Sponsor and the FDA.

Consent Materials

A template informed consent addendum is attached for all subjects currently active in the FIX-HF-5 protocol.

The Statistical Analysis Report for the FIX-HF-5 Clinical Study of the OPTIMIZER System in Patients with Medically Refractory Heart Failure

By

[name].

I. Introduction

Moderate to severe heart failure is associated with disability that significantly limits exercise tolerance and is associated with poor quality of life. The OPTIMIZER System delivers cardiac contractility modulation, non-excitatory signals during the myocardial absolute refractory period synchronized with locally sensed electrical activity, intended to improve symptoms in treated subjects.

The statistical analysis below provides a detailed description of the analyses conducted, hypotheses tested, the precise statistical methods used and the populations analyzed. The analysis methods provide a thorough evaluation of the OPTIMIZER System in the population of moderate to severe heart failure subjects.

II. Study Design

This is a multicenter, randomized, prospective, parallel group clinical trial to evaluate the safety and efficacy of the OPTIMIZER™ System with active fixation leads in subjects with moderate to severe heart failure. Four hundred and twenty eight (428) subjects from 50 centers in the US were randomized with equal probability to implantation of the OPTIMIZER™ System in combination with optimal medical treatment (OMT) for heart failure or to OMT alone. Randomization used permuted blocks of four and was stratified by center and etiology of heart failure (ischemic versus non-ischemic cardiomyopathy). The nature of the treatment and requirement for one-year follow up precluded blinding of subjects and their treating clinicians, however, safety data were adjudicated by an independent committee of physician experts according to pre-specified criteria.

III. Objective

The objective of this investigation was to evaluate the safety and effectiveness of the OPTIMIZER™ System with active fixation leads in subjects with moderate to severe heart failure.

IV. Study Sites and Patient Distribution

The distribution of patients by study site and treatment group is given in the table below.

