Variable	Missing Mean (SD) N Med (Min, Max)	Non-Missing Mean (SD) N Med (Min, Max)	P-value
Age (yrs)	55.65 (14.42) 80 56.5 (19, 82)	58.93 (11.95) 348 59 (26, 86)	0.0673 ²
QRS Duration (ms) ³	100.11 (14.03) 80 98.5 (72, 150)	101.91 (14.12) 346 102 (60, 150)	0.1325 ¹
PR Interval ⁴	175.45 (34.00) 80 174.0 (24, 248)	181.70 (31.53) 345 180.0 (65, 272)	0.2284 ¹
Holter (PVCs/24hr)	1521.9 (2160.1) 80 438.6 (0, 8527.0)	1303.2 (1916.7) 348 411.6 (0, 9960.5)	0.4565 ²
LVEF (%) (site)	26.50 (6.42) 80 27 (11, 35)	25.78 (6.60) 348 25.5 (10, 40)	0.3368 ¹
LVEDD (mm) (site) ⁵	62.31 (8.58) 80 62 (42, 89)	62.80 (8.98) 346 63 (30, 88)	0.7555 ¹
MLWHFQ	58.86 (22.73) 80 60 (2, 96)	58.96 (22.90) 348 63 (0, 102)	0.8365 ¹
6MW (meters) ⁶	321.96 (88.40) 79 334.0 (95, 585)	325.93 (87.15) 348 326 (80, 600)	0.7243 ¹
CPX (site) ⁷			
Peak VO2 (ml/kg/min)	14.60 (3.36) 79 14.2 (6.0, 25.9)	14.80 (2.96) 348 14.95 (9.0, 22.5)	0.4583 ¹
RER	1.14 (0.09) 79 1.13 (0.91, 1.43)	1.13 (0.10) 348 1.12 (0.96, 1.64)	0.2218 ¹
Exercise Time (minutes)	11.13 (3.49) 79 10.53 (4.0, 18.33)	11.58 (3.38) 348 11.75 (2.73, 22.00)	0.2186 ¹
Physical Exam			
Weight (kg)	90.31 (23.99) 80 90.00(47.3, 140.9)	92.67 (22.44) 348 90.00 (44.7, 184.5)	0.3656 ¹
Height (cm)	173.11 (10.84) 80 174.5 (142.0, 192.0)	173.02 (9.42) 348 173.0 (142.0 201.0)	0.5592 ¹
BMI (kg/m2)	30.02 (7.37) 80 28.98 (18.38, 60.99)	30.85 (6.65) 348 30.18 (18.63, 61.09)	0.1955 ¹
Resting HR (bpm) ⁸	75.76 (12.11) 80 76.0 (50.0, 107.0)	73.42 (12.75) 347 72.0 (46.0, 118.0)	0.0655 ¹
SBP (mmHg) ⁸	117.15 (19.03) 80 118 (78, 178)	115.89 (18.46) 347 114 (78, 195)	0.4532 ¹
DBP (mmHg) ⁸	71.56 (12.63) 80 70.0 (48.0, 110.0)	70.67 (10.97) 347 70.0 (42.0, 119.0)	0.7129 ¹
MBP ⁸	86.76 (13.61) 80 87.00 (59.33, 132.67)	85.74 (12.29) 347 84.67 (54.67, 144.33)	0.5171 ¹

¹Two-sided Wilcoxon rank sum test.²Two-sided unequal variance two-sample t-test.³Two patients with non-missing data did not report QRS duration.⁴Three patients with non-missing data did not report a PR interval.⁵Two patients with non-missing data did not report LVEDD.⁶One patient with missing data did not have a 6 minute walk time at baseline.⁷One patient with missing data did not have any variable reported for the Site CPX.⁸One patient with non-missing data did not report heart rate or blood pressure at baseline.

Thus, there are no statistically significant differences in the quantitative baseline characteristics between the missing and non-missing patients.

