Table VIII.2 Baseline Demographics and Medical History Categorical Variables - Compare Patients with Missing 24 Week AT data with those Not Missing 24 Week Data

Variable	Missing n/N (%)	Non Missing n/N (%)	P- value ¹
Male	58/80 (72.50)	251/348 (72.13)	1.0000
Ethnicity (White)	52/80 (65.00)	244/348 (70.11)	0.4207
CHF Etiology (Ischemic)	32/80 (40.00)	115/348 (33.05)	0.2426
Prior MI	44/80 (55.00)	207/348 (59.48)	0.5292
Prior CABG	30/80 (37.50)	138/348 (39.66)	0.7998
Prior PCI	30/80 (37.50)	139/348 (39.94)	0.7058
Diabetes	38/80 (47.50)	155/348 (44.54)	0.7088
NYHA (site) (Class IV)	11/80 (13.75)	37/348 (10.63)	0.4334

¹Two-sided Fisher's exact test.

Table VIII.3 Baseline Medications - Compare Patients with Missing 24 Week AT data with those Not Missing 24 Week Data

Medication	Missing n/N (%)	Non-Missing n/N (%)	P-Value ¹
Angiotensin converting enzyme inhibitor (ACEi)	58/80 (72.50)	243/348 (69.83)	0.6856
Angiotensin receptor blocker (ARB)	18/80 (22.50)	85/348 (24.43)	0.7733
ACEi or ARB	72/80 (90.00)	318/348 (91.38)	0.6660
Beta Blocker	72/80 (90.00)	328/348 (94.25)	0.2060
Loop Diuretic	76/80 (95.00)	316/348 (90.80)	0.2701
Second Diuretic	9/80 (11.25)	22/348 (6.32)	0.1489
Aldosterone Inhibitor	35/80 (43.75)	162/348 (46.55)	0.7096
Hydralazine	7/80 (8.75)	20/348 (5.75)	0.3122
Nitrates	27/80 (33.75)	121/348 (34.77)	0.8970
Calcium Channel Blocker	4/80 (5.00)	23/348 (6.61)	0.7994
Anti-arrhythmic	4/80 (5.00)	61/348 (17.53)	0.0031

¹Two-sided Fisher's exact test.

Only anti-arrhythmic medication use was statistically significantly difference between the missing and non-missing groups. The non-missing group had the higher rate of anti-arrhythmic medication use.

Table VIII.4 Baseline Cardiopulmonary Exercise (Core Laboratory) - Compare Patients with Missing 24 Week AT data with those Not Missing 24 Week Data

Variable	Control Mean (SD) N Med (Min, Max)	Optimizer Mean (SD) N Med (Min, Max)	P –value
Duration (minutes) ³	11.22 (3.50) 80 10.48 (4.92, 18.82)	11.47 (3.29) 347 11.65 (2.73, 20.13)	0.3570 ¹
Peak SBP (mmHg) ⁴	139.9 (24.3) 80 140 (96, 210)	139.1 (26.2) 343 140 (72, 240)	0.7116 ¹
Peak HR (bpm) ⁵	124.0 (20.4) 80 123.5 (72, 173)	121.1 (20.3) 346 121 (72, 176)	0.2372 ¹
Peak VO2 (ml/kg/min) ⁶	14.69 (2.99) 78 14.65 (8.4, 21.7)	14.73 (3.00) 347 14.80 (8.5, 23.0)	0.8189 ¹
Peak RER ⁷	1.13 (0.11) 79 1.12 (0.89, 1.52)	1.13 (0.09) 347 1.12 (0.97, 1.57)	0.7702 ²
AT (ml/kg/min) ⁸	11.00 (1.99) 64 10.6 (7.4, 15.6)	10.95 (2.25) 344 10.7 (5.3, 17.0)	0.7541 ¹

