¹Two-sided Wilcoxon rank sum test.

²Two-sided unequal variance two-sample t-test.

³One non-missing patient did not have a core lab report on exercise duration.

⁴Five non-missing patients did not have core lab report of baseline peak SBP.

⁵Two non-missing patients did not have core lab report of peak heart rate.

⁶Two missing patients and one non-missing patient did not have a core lab report of peak VO2.

⁷One missing patient and one non-missing patient did not have a core lab report of peak RER.

⁸Sixteen missing patients and four non-missing patients did not have a core lab report of AT.

Exercise testing was not statistically significantly different between the missing and non-missing patients after deleting missing patients with less than 6.5 minute of baseline exercise duration. These tests do not provide evidence that the missing at random assumption for the imputations below is violated.

IX. Imputation Methods

There are several methods of imputation that could be applied to missing data based on what data are missing and the relationships of the missing observations to data that are present. The proposed method of imputation depends on the amount of data that are present for any given subject as summarized in the following table, and detailed below.

Table IX.1 Imputation Cases from Statistical Analysis Plan

CASE	Baseline		6 Month Follow-Up		Imputation Method	Patients in Case	
	Peak VO2	AT	Peak VO2	AT		Treatment	Control
0	Present	Present	Present	Present	None	159	153
1	Present	Present	Present	Absent	Stochastic regression based on PVO2 and RER at 6M	8	9
2	Present	Absent	Present	Present	Stochastic regression based on PVO2 and RER at Baseline	10	2
3	Present	Absent	Present	Absent	Stochastic regression based on Δ PVO2 and RER	1	0
4	Present	Present	Absent	Absent	Propensity Matching and Random Selection	18	29
5	Present	Absent	Absent	Absent	Propensity Matching and Random Selection	1	2
6	Patients died, had an event, or had missing data and baseline duration <6.5 minutes ¹					18	18

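### The tables offered as support for missing at random did not drop the 13 short-exercise patients; they moved them, with every other worst-score patient, into the non-missing comparator

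*Combined protocol and SAP*

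**What the plan says.** Section VIII of the statistical analysis report explains that a first comparison found baseline exercise duration related to missingness, so that strictly the data were not missing at random. The remedy was to give a worst score to patients with missing week-24 data and a core-laboratory baseline exercise time under 6.5 minutes (5 Active, 8 Control). They join 23 patients with an event in imputation Case 6.

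The comparison is then repeated: "After removing the 13 cases with missing 24 week data and an exercise time less than 6.5 minutes", the baseline characteristics of "patients with missing and non-missing data at 24 weeks or baseline are presented in the following tables". Tables VIII.1 to VIII.3 have a Missing and a Non-missing column. Table VIII.4 has the same split, but its columns are headed Control and Optimizer. All four titles describe the split as missing against not missing week-24 AT data.

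The section concludes: "Exercise testing was not statistically significantly different between the missing and non-missing patients after deleting missing patients with less than 6.5 minute" of baseline exercise. It adds that the tests give no evidence against missing at random. The footnote to Table IX.1 goes further. It says that giving these patients worst-case values and taking them out of the comparison left no significant difference, and that this demonstrates the assumption is not violated.

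**The concern.** Randomization covered 428 patients (Section II: "Four hundred and twenty eight (428) subjects from 50 centers in the US were randomized"). If 13 had been removed, the tables should total 415, yet they total 428. Nor do the column sizes match the titles, because week-24 AT was observed in 327 patients, not 348.

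These tables are the stated evidence for two claims: that the 6.5-minute remedy dealt with the exercise-duration imbalance, and that missing at random is tenable for the patients imputed in the primary effectiveness analysis. If the patients who caused the imbalance were put into the reference group, the test is tilted towards finding no difference. The same count, 348, reappears in Table IX.4 as the pool of patients with actual data from which values are drawn for Cases 4 and 5. The make-up of that group may therefore matter beyond the descriptive tables.

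**Working it through.** **1. Reproduce the printed columns.** The column sizes are 80 and 348 (Table VIII.2, male: "58/80 (72.50) 251/348 (72.13"). Table IX.1 gives, Treatment + Control:

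| Case | Count | Baseline AT | Week-24 AT |
|---|---|---|---|
| 0 | 159 + 153 = 312 | present | present |
| 1 | 8 + 9 = 17 | present | absent |
| 2 | 10 + 2 = 12 | absent | present |
| 3 | 1 + 0 = 1 | absent | absent |
| 4 | 18 + 29 = 47 | present | absent |
| 5 | 1 + 2 = 3 | absent | absent in 1, present in 2 (Section IX.b text) |
| 6 | 18 + 18 = 36 | mixed | see step 4 |

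The Case 1 row, for instance, reads "Stochastic regression based on PVO2 and RER at 6M 8 9".

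- Cases 1 to 5: 17 + 12 + 1 + 47 + 3 = 80, the Missing column.
- Case 0 + Case 6: 312 + 36 = 348, the Non-missing column.
- No other combination of whole cases sums to 80.

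**2. Confirm with independent counts.**

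- Baseline AT is absent in 6 Control + 14 Optimizer = 20 patients (Table VI.4 footnote). Cases 2, 3 and 5 hold 12 + 1 + 3 = 16 of them. The other 4 must be in Case 6, since Cases 0, 1 and 4 have baseline AT. The Table VIII.4 footnote prints 16 in Missing and 4 in Non-missing, an exact match.
- In Table IX.4, 378 patients outside Cases 4 and 5 less 348 not missing leaves 30 = Cases 1 to 3 (17 + 12 + 1).

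**3. Locate the 13.** Section VIII builds the worst-score group as 10 + 3 + 5 = 18 Active and 4 + 6 + 8 = 18 Control and labels it Case 6. The 13 (5 + 8) are part of it, so they are in the Non-missing column. Dropping them would give 80 against 348 − 13 = 335, total 415.

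**4. Count week-24 AT in each column.** Table XIII.1a shows it observed in 158 Control + 169 Optimizer = 327, so 428 − 327 = 101 lack it.

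- Outside Case 6, those lacking it are Cases 1, 3 and 4 and one patient in Case 5: 17 + 1 + 47 + 1 = 66.
- The remaining 101 − 66 = 35 are in Case 6, that is, 35 of 36.
- By arm: Optimizer 159 (Case 0) + 10 (Case 2) = 169, as printed. Control 153 + 2 (Case 2) + 2 (Case 5) = 157, one short of 158. That patient also appears in the Control change-score count, 154 against 153 in Case 0.
- Conversely, 12 (Case 2) + 2 (Case 5) = 14 of the 80 Missing patients do have a week-24 AT.

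A split that matched the titles would be 101 against 327.

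**5. Effect on the duration comparison.** Table VIII.4 prints core-laboratory duration as mean 11.22 (SD 3.50, n = 80) against 11.47 (SD 3.29, n = 347), a gap of 0.25 minutes, Wilcoxon p = 0.3570. The durations of the 13 are not given. Assume a mean of 4.0 to 6.4 minutes and SD 0.8, with a Welch t-test standing in for the Wilcoxon test:

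- Comparator mean without the 13: (347 × 11.47 − 13 × m)/334, which is 11.76 for m = 4.0 and 11.67 for m = 6.4. The gap becomes 0.54 to 0.45 minutes, p about 0.21 to 0.30.
- With the 13 in the Missing column (93 against 334): p about 0.001 to 0.008.
- As printed, the same t-test gives p = 0.56.

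The step to non-significance comes mainly from taking the 13 out of the Missing column. Adding them to the comparator roughly halves the gap that remains.

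**6. The claim of no significant difference.** Table VIII.3 gives anti-arrhythmic use as 4/80 (5.00%) against 61/348 (17.53%), p = 0.0031; Fisher's exact test on these counts reproduces it. The text below that table acknowledges the difference, but the Table IX.1 footnote does not. Neither anti-arrhythmic use nor exercise duration is among the covariates in Table IX.3.

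**The case against.** Several points on the other side are sound.

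- The introduction to the tables says the grouping concerns data missing at week 24 or at baseline. That explains why Case 2 is in the Missing column and why the count is not 101. On this view the titles are loose shorthand.
- The 80 are exactly the patients whose values are imputed by regression or propensity matching. Case 6 patients get fixed worst scores and do not rely on missing at random.
- On the indicative check, duration would probably still be non-significant with the 13 fully dropped.
- One significant result among 18 + 8 + 11 + 6 = 43 tests is unremarkable: 43 × 0.05 is about 2.

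These points limit the consequences. They do not make a comparator containing 35 patients without the primary variable a non-missing group, and they do not reconcile a table of 428 with a stated deletion of 13.

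Two stronger readings are tempting, and the documents support neither.

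- A reader might infer that the 13 are still in the Missing column, because its shortest tests are under 6.5 minutes: "11.22 (3.50) 80 10.48 (4.92, 18.82" by core laboratory and "11.13 (3.49) 79 10.53 (4.0, 18.33" by site. The rule also requires missing week-24 data. A Case 2 patient with a short test has week-24 data and is not one of the 13, and the site figure is not the one the rule uses.
- A reader might infer that the columns are split on week-24 peak VO2, because 169 + 179 = 348 patients have it. That split would put the 12 + 1 = 13 patients of Cases 2 and 3 in Non-missing without a baseline AT, where the footnote says 4. It would leave at most 3 + 4 = 7 such patients in Missing, where the footnote says 16. The match on 348 is a coincidence.

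**Conclusion.** The point stands as a defect in the evidence offered and in its labelling. The report says 13 patients were deleted; they were reclassified into the comparator. All 36 worst-score patients are there (36/348 = 10% of the column), and 35 of them have no observed week-24 AT. The titles are wrong in both directions, since 14 of the 80 Missing patients have one. The non-significant duration result therefore cannot be cited as showing that the 6.5-minute remedy worked, and the footnote's claim of no significant difference contradicts Table VIII.3.

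The column make-up rests on the case counts in Table IX.1, corroborated by the baseline-AT footnotes and Table IX.4. The figure of 35 also relies on the Section IX.b description of the three Case 5 patients, and the arm-level counts agree with it. The duration p-values rest on an assumed mean and SD for the 13 and on a t-test, so they are indicative only. The effect of removing all 36 is unknown.

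A reader might go further and infer that the imputation is invalid or that the primary effectiveness result would change. The documents do not show that. Equally, baseline comparisons of this kind cannot establish missing at random, however the groups are formed. Whether the 36 also served as donors for Cases 4 and 5 is an open question, not a finding.

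**What to change.** 1. Re-run Tables VIII.1 to VIII.4 as Cases 1 to 5 (80) against Case 0 (312), with Case 6 (36) excluded or in its own column.
2. Retitle the tables to state that grouping, and correct the Control and Optimizer column headings of Table VIII.4 to Missing and Non-missing.
3. Replace the wording on removal or deletion of the 13 with what was done. Replace the statement that missing at random is demonstrated with what the re-run tables show, including anti-arrhythmic use.
4. Reconsider the propensity covariates in Table IX.3; exercise duration and anti-arrhythmic use are the obvious candidates.
5. State whether the 348 donors in Table IX.4 include the 36 Case 6 patients. If they do, limit donors to observed values and repeat the imputation for Cases 4 and 5.

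The cost is a re-run of four descriptive tables, plus any re-imputation that items 4 and 5 require. The conclusion on exercise duration may not change, but it would then rest on the comparison the text describes.
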